5.1.1.7 Food Effect

Administration with a low-fat meal increased venetoclax exposure by approximately 3.4-fold and administration with a high-fat meal increased venetoclax exposure by 5.1- to 5.3-fold compared with fasting conditions. Venetoclax should be administered with a meal as described in Section 4.3.2.1.

5.1.1.8 Concomitant Use with Other Medications

Specific recommendations are provided for co-administration of venetoclax with other medications, including inhibitors and inducers of CYP3A (see Section 4.4).

Live, attenuated vaccines should not be administered prior to, during, or after treatment with venetoclax until B-cell recovery occurs. The safety and efficacy of immunization

with live, attenuated vaccines during or following venetoclax therapy have not been studied. Patients should be advised that vaccinations may be less effective.

Due to possible CYP3A mediated metabolic interaction, certain food items (e.g., grapefruit and Seville oranges) should not be consumed during treatment with venetoclax. Further details of excluded food items are provided in Section 4.4.

5.1.2 Safety Plan for Fulvestrant

Fulvestrant is an ER antagonist indicated for the treatment of HR+ MBC in postmenopausal women with disease progression following anti-estrogen therapy.

In a study with postmenopausal women with advanced breast cancer who had disease recurrence on or after adjuvant endocrine therapy or progression following endocrine therapy for advanced disease, the most frequently reported adverse events were injection-site pain (11.6% of patients), nausea (9.7%), and bone pain (9.4%). Because fulvestrant is administered intramuscularly, it should be used with caution in patients with bleeding diatheses, thrombocytopenia, or anticoagulant use. For details regarding the safety profile of fulvestrant, refer to the local prescribing information.

There are no expected clinically significant overlapping toxicities between venetoclax and fulvestrant. Routine safety monitoring and periodic laboratory tests for the fulvestrant and venetoclax combination will occur throughout the study.

Fulvestrant should not be administered to pregnant women and it must be discontinued if a female patient becomes pregnant. Please refer to Section 4.1.1 and Section 4.1.2 for further details on study eligibility and contraceptive requirements for patients.

5.1.3 Management of Patients Who Experience Specific Adverse Events

5.1.3.1 Dose Modifications

The fulvestrant dose level cannot be modified. In general, the investigator may consider continuing fulvestrant if the observed adverse event is not thought to be fulvestrant-related.

See Section 5.1.3.3 for dose delay or modification guidelines of venetoclax.

5.1.3.2 Treatment Interruption

Patients who interrupt all study treatments secondary to treatment-related adverse events for longer than 28 days should discontinue all study drugs, although they are to continue being followed for disease progression as described in Appendix 1. However, patients who are deriving benefit from the treatment may continue treatment at the investigator's discretion based upon the risk/benefit balance.

As of 8 October 2020, venetoclax will no longer be administered to patients in the study.

Patients who discontinue fulvestrant should also discontinue venetoclax, although they are to continue evaluation per protocol.

5.1.3.3 Management Guidelines

Guidelines for management of specific adverse events are outlined in [Table 3](#).

Recommendations for the initial management of electrolyte imbalances and prevention of TLS are provided in [Appendix 8](#). Additional guidelines are provided in the subsections below.

Table 3 Guidelines for Management of Patients Who Experience Specific Adverse Events

Event	Action to Be Taken
Grade 3 or 4 (NCI grading scale) neutropenia with or without fever and infection	
 • Withhold venetoclax for at least 7 days. • Administer treatment including G-CSF or growth factors for neutropenia as indicated. • When counts recover to ANC $\geq 1 \times 10^9/L$ resume venetoclax at one dose-level reduction.
Grade 3 thrombocytopenia with symptomatic bleeding or Grade 4 thrombocytopenia	
 • Withhold venetoclax for Grade 4 thrombocytopenia or Grade 3 in presence of symptomatic bleeding until resolution of bleeding. Platelets may be transfused at the discretion of the investigator. When platelet level rises to $\geq 75,000/\mu L$ without transfusional support, restart venetoclax at previous dose. • For a second episode of severe thrombocytopenia and/or symptomatic bleeding, withhold venetoclax. When platelet level rises to $\geq 75,000/\mu L$ without transfusional support, restart venetoclax at one dose-level reduction. • For subsequent episodes of severe thrombocytopenia, withhold venetoclax. When platelet level rises to $\geq 75,000/\mu L$ without transfusional support, restart venetoclax at one dose-level reduction. • For recurrent severe thrombocytopenia in spite of dose reduction and/or symptomatic bleeding, consult the Medical Monitor regarding continuation on the protocol.
Non-hematologic toxicity	
Grade 3 or 4 non-hematologic events not specifically described above	
 • Delay venetoclax for a maximum of 28 days. 
 First episode: If improvement to Grade ≤ 1 or baseline, resume previous doses of venetoclax. For subsequent episodes: If improvement to Grade ≤ 1 or baseline, restart venetoclax at one dose-level reduction. • Certain treatment emergent non-hematologic adverse events (e.g., venous thromboembolic events) may be managed and become clinically stable following medical intervention but may not improve to Grade ≤ 1 according to the NCI CTCAE definitions. In such cases, if a patient is clinically stable, resumption of study drug may be possible after consultation with the Medical Monitor.

Table 3 Guidelines for Management of Patients Who Experience Specific Adverse Events (cont.)

Event	Action to Be Taken
Grade 2 non-hematologic toxicity	
 • Delay treatment with venetoclax until resolution to Grade \leq 1 (or baseline status) for a maximum of 28 days. • After resolution, resume full dose of venetoclax
Grade 1 non-hematologic toxicity	
 • There is no dose reduction or delay.

CTCAE=Common Terminology Criteria for Adverse Events; G-CSF=granulocyte stimulating factor; NCI=National Cancer Institute.

Although patients with adverse events are to be managed according to the particular clinical circumstances based on the investigator's medical judgement, dose reduction of venetoclax by one and, if needed, two dose levels will be allowed depending on the type and severity of the toxicity encountered. Each dose reduction of venetoclax will occur by 200 mg (e.g., the starting dose of 800 mg will be reduced to 600 mg, then to 400 mg. If a third dose reduction is necessary (from 400 mg to 200 mg) this should be discussed with the Medical Monitor. Patients who require venetoclax dose reduction below 200 mg should discontinue venetoclax. Such patients may continue to receive fulvestrant at the discretion of the investigators. Patients requiring clarification regarding management of adverse events and dosing and all patients requiring more than two dose reductions should be discussed with the Medical Monitor. All dose modifications/adjustments must be clearly documented in the patient's source notes and eCRF.

Once a dose has been reduced for a given patient, all subsequent cycles should be administered at the reduced dose level, unless further dose reduction is allowed. Dose re-escalation is not allowed.

5.2 SAFETY PARAMETERS AND DEFINITIONS

Safety assessments will consist of monitoring and recording adverse events, including serious adverse events and adverse events of special interest, performing protocol-specified safety laboratory assessments, measuring protocol-specified vital signs, and conducting other protocol-specified tests that are deemed critical to the safety evaluation of the study.

Certain types of events require immediate reporting to the Sponsor, as outlined in Section 5.4.

5.2.1 Adverse Events

According to the ICH guideline for Good Clinical Practice, an adverse event is any untoward medical occurrence in a clinical investigation subject administered a

pharmaceutical product, regardless of causal attribution. An adverse event can therefore be any of the following:

- Any unfavorable and unintended sign (including an abnormal laboratory finding), symptom, or disease temporally associated with the use of a medicinal product, whether or not considered related to the medicinal product
- Any new disease or exacerbation of an existing disease (a worsening in the character, frequency, or severity of a known condition) (see Section 5.3.5.9 and Section 5.3.5.10 for more information)
- Recurrence of an intermittent medical condition (e.g., headache) not present at baseline
- Any deterioration in a laboratory value or other clinical test (e.g., ECG, X-ray) that is associated with symptoms or leads to a change in study treatment or concomitant treatment or discontinuation from study drug
- Adverse events that are related to a protocol-mandated intervention, including those that occur prior to assignment of study treatment (e.g., screening invasive procedures such as biopsies)

5.2.2 Serious Adverse Events (Immediately Reportable to the Sponsor)

A serious adverse event is any adverse event that meets any of the following criteria:

- Is fatal (i.e., the adverse event actually causes or leads to death)
- Is life threatening (i.e., the adverse event, in the view of the investigator, places the patient at immediate risk of death)
 - This does not include any adverse event that, had it occurred in a more severe form or was allowed to continue, might have caused death.
- Requires or prolongs inpatient hospitalization (see Section 5.3.5.11)
- Results in persistent or significant disability/incapacity (i.e., the adverse event results in substantial disruption of the patient's ability to conduct normal life functions)
- Is a congenital anomaly/birth defect in a neonate/infant born to a mother exposed to study drug
- Is a significant medical event in the investigator's judgment (e.g., may jeopardize the patient or may require medical/surgical intervention to prevent one of the outcomes listed above)

The terms "severe" and "serious" are not synonymous. Severity refers to the intensity of an adverse event (e.g., rated as mild, moderate, or severe, or according to NCI CTCAE; see Section 5.3.3); the event itself may be of relatively minor medical significance (such as severe headache without any further findings).

Severity and seriousness need to be independently assessed for each adverse event recorded on the eCRF.

Serious adverse events are required to be reported by the investigator to the Sponsor immediately (i.e., no more than 24 hours after learning of the event; see Section 5.4.2 for reporting instructions).

5.2.3 Adverse Events of Special Interest (Immediately Reportable to the Sponsor)

Adverse events of special interest are required to be reported by the investigator to the Sponsor immediately (i.e., no more than 24 hours after learning of the event; see Section 5.4.2 for reporting instructions). Adverse events of special interest for this study are as follows:

- Cases of potential drug-induced liver injury that include an elevated ALT or AST in combination with either an elevated bilirubin or clinical jaundice, as defined by Hy's Law (see Section 5.3.5.7)
- Suspected transmission of an infectious agent by the study drug, as defined below:

Any organism, virus, or infectious particle (e.g., prion protein transmitting transmissible spongiform encephalopathy), pathogenic or non-pathogenic, is considered an infectious agent. A transmission of an infectious agent may be suspected from clinical symptoms or laboratory findings that indicate an infection in a patient exposed to a medicinal product. This term applies only when a contamination of the study drug is suspected.
- TLS

5.3 METHODS AND TIMING FOR CAPTURING AND ASSESSING SAFETY PARAMETERS

The investigator is responsible for ensuring that all adverse events (see Section 5.2.1 for definition) are recorded on the Adverse Event eCRF and reported to the Sponsor in accordance with instructions provided in this section and in Section 5.4, Section 5.5, and Section 5.6.

For each adverse event recorded on the Adverse Event eCRF, the investigator will make an assessment of seriousness (see Section 5.2.2 for seriousness criteria), severity (see Section 5.3.3), and causality (see Section 5.3.4).

5.3.1 Adverse Event Reporting Period

Investigators will seek information on adverse events at each patient contact. All adverse events, whether reported by the patient or noted by study personnel, will be recorded in the patient's medical record and on the Adverse Event eCRF.

After informed consent has been obtained but prior to initiation of study drug, only serious adverse events caused by a protocol-mandated intervention (e.g., invasive procedures such as biopsies, discontinuation of medications) should be reported (see Section 5.4.2 for instructions for reporting serious adverse events).

After initiation of study drug, all adverse events will be reported through 28 days after the last dose of study drug (venetoclax or fulvestrant, whichever is later). After this period, investigators should report any deaths, serious adverse events, or other adverse events of concern that are believed to be related to prior study drug treatment as prescribed in Section 5.6.

Instructions for reporting adverse events that occur after the adverse event reporting period are provided in Section 5.6.

5.3.2 Eliciting Adverse Event Information

A consistent methodology of non-directive questioning should be adopted for eliciting adverse event information at all patient evaluation timepoints. Examples of non-directive questions include the following:

"How have you felt since your last clinic visit?"

"Have you had any new or changed health problems since you were last here?"

5.3.3 Assessment of Severity of Adverse Events

The adverse event severity grading scale for the NCI CTCAE v5.0 will be used for assessing adverse event severity. Table 4 will be used for assessing severity for adverse events that are not specifically listed in the NCI CTCAE.

Table 4 Adverse Event Severity Grading Scale for Events Not Specifically Listed in NCI CTCAE

Grade	Severity
1	Mild; asymptomatic or mild symptoms; clinical or diagnostic observations only; or intervention not indicated
2	Moderate; minimal, local, or non-invasive intervention indicated; or limiting age-appropriate instrumental activities of daily living ^a
3	Severe or medically significant, but not immediately life-threatening; hospitalization or prolongation of hospitalization indicated; disabling; or limiting self-care activities of daily living ^{b, c}
4	Life-threatening consequences or urgent intervention indicated ^d
5	Death related to adverse event ^d

NCI CTCAE = National Cancer Institute Common Terminology Criteria for Adverse Events.

Note: Based on the most recent version of NCI CTCAE (v5.0), which can be found at: https://ctep.cancer.gov/protocolDevelopment/electronic_applications/ctc.htm

- ^a Instrumental activities of daily living refer to preparing meals, shopping for groceries or clothes, using the telephone, managing money, etc.
- ^b Examples of self-care activities of daily living include bathing, dressing and undressing, feeding oneself, using the toilet, and taking medications, as performed by patients who are not bedridden.
- ^c If an event is assessed as a "significant medical event," it must be reported as a serious adverse event (see Section 5.4.2 for reporting instructions), per the definition of serious adverse event in Section 5.2.2.
- ^d Grade 4 and 5 events must be reported as serious adverse events (see Section 5.4.2 for reporting instructions), per the definition of serious adverse event in Section 5.2.2.

5.3.4 Assessment of Causality of Adverse Events

Investigators should use their knowledge of the patient, the circumstances surrounding the event, and an evaluation of any potential alternative causes to determine whether an adverse event is considered to be related to the study drug, indicating "yes" or "no" accordingly. The following guidance should be taken into consideration (see also [Table 5](#)):

- Temporal relationship of event onset to the initiation of study drug
- Course of the event, with special consideration of the effects of dose reduction, discontinuation of study drug, or reintroduction of study drug (as applicable)
- Known association of the event with the study drug or with similar treatments
- Known association of the event with the disease under study
- Presence of risk factors in the patient or use of concomitant medications known to increase the occurrence of the event
- Presence of non-treatment-related factors that are known to be associated with the occurrence of the event

Table 5 Causal Attribution Guidance

Is the adverse event suspected to be caused by the study drug on the basis of facts, evidence, science-based rationales, and clinical judgment?	
YES	There is a plausible temporal relationship between the onset of the adverse event and administration of the study drug, and the adverse event cannot be readily explained by the patient's clinical state, intercurrent illness, or concomitant therapies; and/or the adverse event follows a known pattern of response to the study drug; and/or the adverse event abates or resolves upon discontinuation of the study drug or dose reduction and, if applicable, reappears upon re-challenge.
NO	An adverse event will be considered related, unless it fulfills the criteria specified below. Evidence exists that the adverse event has an etiology other than the study drug (e.g., preexisting medical condition, underlying disease, intercurrent illness, or concomitant medication); and/or the adverse event has no plausible temporal relationship to administration of the study drug (e.g., cancer diagnosed 2 days after first dose of study drug).

For patients receiving combination therapy, causality will be assessed individually for each protocol-mandated therapy.

5.3.5 Procedures for Recording Adverse Events

Investigators should use correct medical terminology/concepts when recording adverse events on the Adverse Event eCRF. Avoid colloquialisms and abbreviations.

Only one adverse event term should be recorded in the event field on the Adverse Event eCRF.

5.3.5.1 Injection-Site Reactions

Adverse events that occur during or within 24 hours after study drug administration and are judged to be related to study drug injection should be captured as a diagnosis (e.g., "injection-site reaction" on the Adverse Event eCRF. If possible, avoid ambiguous terms such as "systemic reaction." Associated signs and symptoms should be recorded on the dedicated Injection-Site Reaction eCRF. If a patient experiences both a local and systemic reaction to the same dose of study drug, each reaction should be recorded separately on the Adverse Event eCRF, with signs and symptoms also recorded separately on the dedicated Injection-Site Reaction eCRF.

5.3.5.2 Diagnosis versus Signs and Symptoms

For adverse events other than injection-site reactions (see Section 5.3.5.1), a diagnosis (if known) should be recorded on the Adverse Event eCRF rather than individual signs and symptoms (e.g., record only liver failure or hepatitis rather than jaundice, asterixis, and elevated transaminases). However, if a constellation of signs and/or symptoms cannot be medically characterized as a single diagnosis or syndrome at the time of reporting, each individual event should be recorded on the Adverse Event eCRF. If a diagnosis is subsequently established, all previously reported adverse events based on

signs and symptoms should be nullified and replaced by one adverse event report based on the single diagnosis, with a starting date that corresponds to the starting date of the first symptom of the eventual diagnosis.

5.3.5.3 Adverse Events That Are Secondary to Other Events

In general, adverse events that are secondary to other events (e.g., cascade events or clinical sequelae) should be identified by their primary cause, with the exception of severe or serious secondary events. A medically significant secondary adverse event that is separated in time from the initiating event should be recorded as an independent event on the Adverse Event eCRF. For example:

- If vomiting results in mild dehydration with no additional treatment in a healthy adult, only vomiting should be reported on the eCRF.
- If vomiting results in severe dehydration, both events should be reported separately on the eCRF.
- If a severe gastrointestinal hemorrhage leads to renal failure, both events should be reported separately on the eCRF.
- If dizziness leads to a fall and consequent fracture, all three events should be reported separately on the eCRF.
- If neutropenia is accompanied by an infection, both events should be reported separately on the eCRF.

All adverse events should be recorded separately on the Adverse Event eCRF if it is unclear as to whether the events are associated.

5.3.5.4 Persistent or Recurrent Adverse Events

A persistent adverse event is one that extends continuously, without resolution, between patient evaluation timepoints. Such events should only be recorded once on the Adverse Event eCRF. The initial severity (intensity or grade) of the event will be recorded at the time the event is first reported. If a persistent adverse event becomes more severe, the most extreme severity should also be recorded on the Adverse Event eCRF. If the event becomes serious, it should be reported to the Sponsor immediately (i.e., no more than 24 hours after learning that the event became serious; see Section 5.4.2 for reporting instructions). The Adverse Event eCRF should be updated by changing the event from "non-serious" to "serious," providing the date that the event became serious, and completing all data fields related to serious adverse events.

A recurrent adverse event is one that resolves between patient evaluation timepoints and subsequently recurs. Each recurrence of an adverse event should be recorded as a separate event on the Adverse Event eCRF.

5.3.5.5 Abnormal Laboratory Values

Not every laboratory abnormality qualifies as an adverse event. A laboratory test result must be reported as an adverse event if it meets any of the following criteria:

- Is accompanied by clinical symptoms
- Results in a change in study treatment (e.g., dosage modification, treatment interruption, or treatment discontinuation)
- Results in a medical intervention (e.g., potassium supplementation for hypokalemia) or a change in concomitant therapy
- Is clinically significant in the investigator's judgment

Note: For oncology trials, certain abnormal values may not qualify as adverse events.

It is the investigator's responsibility to review all laboratory findings. Medical and scientific judgment should be exercised in deciding whether an isolated laboratory abnormality should be classified as an adverse event.

If a clinically significant laboratory abnormality is a sign of a disease or syndrome (e.g., ALP and bilirubin $5 \times$ ULN associated with cholestasis), only the diagnosis (i.e., cholestasis) should be recorded on the Adverse Event eCRF.

If a clinically significant laboratory abnormality is not a sign of a disease or syndrome, the abnormality itself should be recorded on the Adverse Event eCRF, along with a descriptor indicating whether the test result is above or below the normal range (e.g., "elevated potassium," as opposed to "abnormal potassium"). If the laboratory abnormality can be characterized by a precise clinical term per standard definitions, the clinical term should be recorded as the adverse event. For example, an elevated serum potassium level of 7.0 mEq/L should be recorded as "hyperkalemia."

Observations of the same clinically significant laboratory abnormality from visit to visit should only be recorded once on the Adverse Event eCRF (see Section 5.3.5.4 for details on recording persistent adverse events).

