Safety will be evaluated by monitoring the overall safety events, including all adverse events identified through physical examinations, and assessments of vital signs and laboratory test results. Such events will be graded by the investigators with the use of the National Cancer Institute Common Terminology Criteria for Adverse Events, Version 5.0 (NCI CTCAE v5.0). Safety assessments from laboratory test results will include monitoring of hematology and blood chemistry.

As of 8 October 2020, all active patients in the venetoclax plus fulvestrant arm of the study will be requested to discontinue the venetoclax treatment immediately, and will be given the option to continue fulvestrant treatment alone.

The study schema is presented in [Figure 1](#). A schedule of activities is provided in [Appendix 1](#).

Figure 1 Study Schema

2L = second line; 3L = third line; BC = breast cancer; BCL-2 = B-cell lymphoma 2; CDK4/6i = cyclin-dependent kinase 4/6 inhibitor; ER+ = estrogen receptor-positive; HER2- = human epidermal growth factor receptor-negative; R = randomization.

Note: Stratification is by one vs. two lines of prior therapy in the locally advanced/metastatic setting and BCL-2 High vs. Low (see Section 4.2).

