6.5 SAFETY ANALYSES

The safety analyses will include all randomized patients who received at least one dose of venetoclax or fulvestrant (the safety population) with patients grouped according to the treatment actually received.

Drug exposure will be summarized to include duration of treatment, number of doses, and intensity of dose.

All adverse events occurring during or after the first study drug dose will be summarized by treatment arm and NCI CTCAE grade. In addition, serious adverse events, adverse events of special interest, and adverse events leading to study drug discontinuation or interruption will be summarized accordingly. Multiple occurrences of the same event will be counted once at the maximum severity.

Deaths reported during the study treatment period and those reported during the safety follow-up period will be summarized by treatment arm.

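### Table 3 ties some laboratory grades to a venetoclax hold, so the by-arm difference in those laboratory adverse events may partly reflect reporting; Section 6.5 should add a table of the measured values

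*Combined protocol and SAP*

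**What the plan says.** Four parts of the combined protocol and SAP bear on this.

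- **Reporting rule (Section 5.3.5.5).** A laboratory result must be reported as an adverse event if it comes with symptoms, or "Results in a change in study treatment (e.g., dosage modification, treatment interruption, or treatment discontinuation"), or "Results in a medical intervention (e.g., potassium supplementation for hypokalemia) or a change in concomitant therapy", or "Is clinically significant in the investigator's judgment". The section adds that isolated abnormalities are otherwise left to medical and scientific judgment.
- **Management rule (Section 5.1.3.3, Table 3).** For Grade 3 or 4 neutropenia, whether or not there is fever or infection, the action is "Withhold venetoclax for at least 7 days". Grade 4 thrombocytopenia also leads to a hold; Grade 3 does so only with symptomatic bleeding. For Grade 2 non-hematologic toxicity the action is "Delay treatment with venetoclax until resolution to Grade" 1 or baseline, and Grade 3-4 non-hematologic events also lead to a delay. The table gives no action for fulvestrant, and Section 5.1.3.1 states: "The fulvestrant dose level cannot be modified".
- **Analysis (Section 6.5).** "All adverse events occurring during or after the first study drug dose will be summarized by treatment arm and NCI CTCAE grade". The section also covers exposure, serious events, events of special interest, events leading to discontinuation or interruption, and deaths. It plans no summary of laboratory values.
- **Data collected.** Section 3.1 says: "Safety assessments from laboratory test results will include monitoring of hematology and blood chemistry". Appendix 1 schedules these tests alike in both arms.

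**The concern.** The safety endpoint in the synopsis version of Table 1 is the frequency and severity of adverse events, compared between arms. For that comparison to describe toxicity, the same laboratory value should have about the same chance of becoming an adverse event in either arm. Where Table 3 attaches a venetoclax hold to a grade, following it creates a mandatory reporting criterion that the fulvestrant arm lacks. The trial is open-label, so nothing masks this.

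At stake is how the laboratory adverse event rows are read, above all neutropenia, which Section 5.1.1.2 calls an important identified risk of venetoclax. If more neutropenia is reported on the combination, the planned tables cannot show how much of the excess is lower counts and how much is more complete reporting.

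**Working it through.** The plan states no figure on this point, so there is none to reproduce. The check is a comparison of the rules, followed by an illustration of size.

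**Step 1: one value, two arms.** Take an asymptomatic Grade 3 neutrophil count for which no treatment is given.

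| Section 5.3.5.5 criterion | Venetoclax + fulvestrant | Fulvestrant |
|---|---|---|
| Symptoms | no | no |
| Change in study treatment | yes, if Table 3 is followed | only if the investigator interrupts fulvestrant |
| Intervention or concomitant-therapy change | no | no |
| Investigator's judgment | not needed | the main remaining route |

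The same holds for an asymptomatic Grade 4 platelet count.

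**Step 2: which values are affected.**
- Clearly: Grade 3-4 neutropenia and Grade 4 thrombocytopenia, which Table 3 defines by grade.
- Less clearly: Grade 2 or higher non-hematologic laboratory toxicity, because those rows apply to events or toxicity and so presuppose some classification.
- Not through a specific Table 3 hold: anemia and lymphopenia.
- Not through an asymptomatic value: Grade 3 thrombocytopenia, where the required bleeding meets the symptom criterion in either arm.
- Not where reporting is already mandatory in both arms: liver results meeting Section 5.3.5.7.

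**Step 3: arm sizes.** Section 1.4 reports 19 deaths (37.3%) and 9 deaths (17.3%) among 103 patients. 19/0.373 = 50.9 and 9/0.173 = 52.0, so the arms are 51 and 52, which sum to 103.

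**Step 4: formula.** Let p be the true share of patients, equal in both arms, with at least one asymptomatic, untreated value in an affected grade. Let c and r be the shares of these reported in the combination and fulvestrant arms. The artificial difference is p(c - r). With c = 1 it becomes p(1 - r), an upper bound for given p and r, and the reported ratio is 1/r. The documents give none of p, c or r.

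**Step 5: results with c = 1.**

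| p | r = 100% | r = 90% | r = 75% | r = 50% |
|---|---|---|---|---|
| 5% | 0 | 0.5 points | 1.3 points | 2.5 points |
| 10% | 0 | 1.0 | 2.5 | 5.0 |
| 20% | 0 | 2.0 | 5.0 | 10.0 |
| Ratio 1/r | 1.00 | 1.11 | 1.33 | 2.00 |

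In patients, p = 10% and r = 50% gives 51 × 0.10 = 5.1 against 52 × 0.05 = 2.6 with a reported event, at identical true toxicity. For scale, at p = 20% and r = 50% the standard error is √(0.20 × 0.80/51 + 0.10 × 0.90/52) = 0.070, so the 10-point difference is 1.4 standard errors.

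**Step 6: two qualifications.** If Table 3 is not always followed, the figure shrinks: at p = 20%, c = 90%, r = 50% it is 0.20 × 0.40 = 8 points. If the true rates differ, with control-arm rate q and c = 1, the distortion is q(1 - r). It is then small in absolute terms whenever such values are rare on fulvestrant alone.

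**The case against.** The strongest reply is that Table 3 is guidance for patients who already have an adverse event. Its heading says so, and Section 5.1.3.3 leaves management to the investigator's medical judgement. A reader might infer that every such value is forced into the combination arm's tables, and that isolated ALT or lipase rises behave in the same way. The documents do not support that. A hold is expected, not compelled. For the non-hematologic rows, someone must first regard the value as a toxicity, and Section 5.3.5.5 leaves that to judgment in both arms. This narrows the point but does not remove it: the neutropenia and Grade 4 thrombocytopenia rows are set by grade and need no symptoms, and a hold made under them meets the mandatory criterion.

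Second, an unmodifiable fulvestrant dose does not mean that fulvestrant cannot be interrupted. Section 4.3.2.2 refers to interruption guidelines and Section 5.1.3.2 covers interrupting all study treatments. Growth factor or another intervention also makes reporting mandatory in the control arm. This stands, but no Table 3 grade directs a fulvestrant interruption.

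Third, the consequence is limited. The safety endpoint focuses on serious events, events of special interest and discontinuations. Section 6.5 is descriptive, with no test or threshold. The Internal Monitoring Committee reviews clinically significant laboratory abnormalities, although that is monitoring and not the between-arm analysis. A reader might go further and infer that this asymmetry affected the negative benefit-risk conclusion. It did not on the stated grounds: Section 1.4 rests that conclusion on clinical benefit rate, PFS and deaths.

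Fourth, worst post-baseline grade is not automatically fair either. Appendix 1 draws these tests while treatment continues and, in off-treatment follow-up, only if clinically indicated. The arm treated longer has more chances of a bad value. This is correct and shapes the fix.

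**Conclusion.** The point holds in a limited form. For Grade 3-4 neutropenia and Grade 4 thrombocytopenia, and less clearly for Grade 2 or higher non-hematologic laboratory toxicity, ascertainment of asymptomatic, untreated values is likely to be more complete in the combination arm. Section 6.5 has nothing to offset this. The resulting bias runs against venetoclax.

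Its size is unknown. The illustrated 0 to 10 points rest on assumed p and r, equal true rates and complete reporting in the combination arm. The bias is zero if control-arm investigators report every such value. The documents do not show that a bias has occurred, only that the planned tables could not reveal one. The primary endpoint and the mortality comparison are untouched.

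**What to change.** Add to Section 6.5 that laboratory toxicity will also be compared between arms from the measured scheduled hematology and chemistry values, giving NCI CTCAE grade and shift from baseline for each parameter, whether or not an adverse event was reported. In detail:

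- Present the table by scheduled visit, or over a common early window (for example through a fixed cycle), or alongside exposure, so that unequal treatment duration does not bias worst grade.
- Show unscheduled samples separately, since a hold may prompt more of them.
- Base by-arm statements on neutropenia, platelets and liver tests on this table.
- Add a note to the adverse event tables that laboratory events may be ascertained differently by arm.

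The cost is a few sentences and one set of tables from data already collected. The downside is that unscheduled values drop out of the main comparison. Although venetoclax stopped on 8 October 2020, after the 5 August 2020 cut-off, the tables can still be added to final reporting. Table 3 and patient management stay as they are.
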